2.3. Study groups

There are two groups in this study: intervention (ONBOARD) and control (CGM-only). All participants will receive 12 weeks of CGM supplies and will receive standardized education about getting started with CGM. A person trained in delivering education about CGM will deliver education about CGM use and will be present during a virtual meeting while participant is inserting first sensor during training. This individual will be available to assist with questions from participants. In addition, Dexcom and Abbott representatives are available to participants for technical questions or issues with the system, just like the access any CGM user has. All participants in both groups will be required to actively use CGM for 12 weeks. After that time period, they can continue or discontinue use of CGM. If they decide to continue, the study team will provide information on working with insurance and with their provider to obtain CGM for both study groups.

After randomization, participants in the intervention group will receive 4 one-on-one sessions of ONBOARD (OvercomiNg Barriers & Obstacles to Adopting Diabetes Devices). Sessions will be held every 2-3 weeks over the 12-week period

when participants are using CGM provided by the study. ONBOARD is a multicomponent intervention to provide tailored support for CGM adoption. Session content and strategies are outlined in Table 3. Sessions target four primary topics. Each participant will receive content in the same order, but the program is designed to be flexible depending on individual barriers and concerns. Some participants may spend more time on certain topics than others. ONBOARD will approach CGM data interpretation

Table 3. ONBOARD Intervention Topic Content			
Barrier addressed	Topic name	Strategies used	Goals
	Introduction	- Psychoeducation; rapport building	
 - Provide rationale for ONBOARD - Introduce concepts from Technology Acceptance Model to discuss CGM pros and cons
Physical	Wearing Diabetes Device(s)	- Experiential wear	
 - Troubleshooting device placement - Provide education and examples of problem solving for common concerns and strategies for navigating them: appearance, insertion, skin irritation, discomfort, interference with daily activities - Provide resources for adhesive, skin prep, and adhesive removal
Data	Managing CGM Data	
 - Education - Behavioral: optimizing alert thresholds - Cognitive: Identifying thoughts & feelings 	
 - Provide information on trend arrows - Review options for customizing alert thresholds - Identify common thoughts and feelings that may arise from receiving data (e.g. managing reactions to double arrows) and identify helpful thoughts - Demonstrate how to view data on Clarity or LibreView
Social	CGM and Social Situations	- Problem solving	
 - Demonstrate problem solving common issues that arise with using and wearing diabetes devices around others (e.g. answering questions about devices, engaging with diabetes around others) - Practice using problem-solving exercise in session
Trust	Building Trust	
 - Psychoeducation - Social problem solving 	
 - Demonstrate how others have developed trust and what they do when trust in a device is broken (e.g. listening to body, using meter)
	Wrapping Up	
 - Goal-setting - Motivational Interviewing 	
 - Reviewing perceived benefits of the technology as they relate to, or are weighed against, perceived issues. - Anticipate future barriers that may lead to CGM discontinuation to brainstorm possible alternative actions.

with the goal of reducing 'data overload' and to empower participants to use data in a way that works for them. Setting alerts/alarms, understanding trend arrows, reviewing the data for patterns and trends, and identifying common reactions that may arise with this quantity of glucose data. Participants will first increase comfort with data quantity, change arrows, and alarms, and then will learn to examine data for patterns and trends. Study personnel will not directly suggest insulin dosing and may encourage participants to talk with their care team when relevant. ONBOARD sessions will be delivered individually to participants by a doctoral level

psychologist with diabetes expertise. Each session will include relevant first-person digital stories from adults with T1D, recounting how they managed relevant CGM barriers. Sessions will be delivered via a HIPAA-compliant videoconference program.

2.4. Coordination of study procedures with clinical care

This study will not be directly connected to participants' clinical care. Participants will be encouraged to contact their care providers during the study to pursue initiating CGM use after study supplies run out and participants in the ONBOARD intervention will be provided education on how to advocate for getting the devices they need with their providers and with their insurance companies.

The study staff will have primary role of initiating CGM at the start of the study for all participants and providing training on insertion. Participants will also receive information from study staff on how to share their CGM data with their diabetes providers.

2.5. Study visits and assessments

All participants will attend a baseline study visit. Baseline is the date they complete their first assessment and begin using their CGM and will receive training from study staff on beginning to use CGM. After baseline, only participants randomized to ONBOARD will receive 4 additional study visits. Remaining assessments (A1c, CGM data downloads, and surveys) will be done via mail and electronically, respectively.

Study assessments for both groups will occur at baseline, 3 months, 6 months and 12 months post-baseline. We will conduct these assessments and obtain glucose data to examine changes over time in glycemic and psychosocial variables. Participants will receive a \$25 gift card for each assessment they complete.

Assessment components are included in Table 4.

Table 4. Study Measures

Domain	Measure	Description	0 mos	3 mos	6 mos	12 mos
Demographic	History questionnaire	Medical, personal, device history	X			
	Demographic/medical update	Changes to baseline information		X	X	X
Psychosocial	Diabetes Distress Scale-T1D	28-item validated measure of T1D distress in adults	X	X	X	X
	Fear of Hypoglycemia - Worry	18-items; measure of fears related to severe low BG	X	X	X	X
	Hypoglycemic Confidence Scale	9 items; validated for adults with T1D	X	X	X	X
	Diabetes Self-Compassion Scale	19 items; validated for adults with T1D	X	X	X	X
	Patient Health Questionnaire-8	8 items; assesses depressive symptoms	X	X	X	X
	GAD-7	7 items; assesses anxiety symptoms	X	X	X	X
	Perceived Stress Scale	10 items; assesses stress and coping in past month	X	X	X	X
	World Health Organization-5	5 items; assesses emotional wellbeing	X	X	X	X
	Self Care Inventory-Revised	15 items; measure of a range of self-care activities	X	X	X	X
	Social Support Questionnaire	6 items; assesses availability of social support	X	X	X	X
Technology-specific	Diabetes Empowerment Scale-SF	8 items; assesses diabetes self-efficacy	X	X	X	X
	COVID-related impacts	Assesses general and diabetes-specific impacts of pandemic	X	X	X	X
	INSPIRE survey	Assesses closed loop attitudes	X			X
	Glucose Monitoring System Satisfaction Survey (GMSS-T1D)	15 items; validated measure of glucose monitoring device-related treatment satisfaction and quality of life	X	X	X	X
	Barriers to device use	19-item list of barriers	X	X	X	X
	A1c	Glycemic control	X	X	X	X

A1c and CGM data	% time in range; percent time in hypoglycemia and hyperglycemia; additional indices of variability including standard deviation	Glycemic control from CGM	X	X	X	X
	% time wearing CGM	Data from CGM	X	X	X	X
Satisfaction	Satisfaction survey (for ONBOARD participants only)			X		

2.6. Study population

The participant population is adults with type 1 diabetes ages 18-50. In order to have 76 participants per arm (152 total) we will enroll up to 178 adults with T1D and then randomize them to either the intervention (ONBOARD, n=89) or control group (CGM-only, n=89).

2.6.1. Eligibility criteria

To be eligible for the study, an adult must meet the following criteria:

1. Clinical diagnosis of type 1 diabetes
2. Age between 18 and 50 years at time of screening
3. Comprehension of written and spoken English
4. Lack of consistent continuous glucose monitoring use (>5 days/week) for past 6 months
5. No severe medical conditions, which in the opinion of the investigators are likely to hinder participation in this clinical trial

2.6.2. Exclusion criteria

The presence of any of the following is an exclusion for the study:

1. Subject has a medical disorder that in the judgment of the investigator will interfere with completion of any aspect of the protocol (e.g. pregnancy, kidney disease, skin condition that may hinder sensor application).
2. Subject has a neurologic disorder that in the judgment of the investigator will affect completion of the protocol.

2.7. Data analysis plan

Our team has extensive experience in the use of web-based assessment, data management and data analysis. Quantitative data will be entered into an online encrypted, HIPAA-compliant data management system, REDCap, with secure access for unique study IDs assigned to each participant. REDCap survey data is then ready for download by study staff and will be imported into SPSS for data cleaning and analysis. CGM data will be downloaded via Dexcom Clarity and LibreView which create a CSV file for transfer to REDCap and data analysis programs.

Demographic, medical, psychosocial variables, and some outcome measures are surveys and multi-item scales that participants will answer in REDCap. Psychometric properties of scales will be assessed before proceeding to investigate the proposed aims. These psychometric properties include item-total correlations and Cronbach's α to assess reliability. Total scores and subscale scores, when available, will be calculated and used for statistical analyses. Descriptive statistics will calculate frequencies, means and standard deviations for study variables. Independent samples t-tests and χ^2 analyses will assess potential differences between groups at baseline in demographic, psychosocial and diabetes variables. Analyses for Hypotheses 1&2 will follow the intention-to-treat principle.

To test Hypotheses 1&2, we will first conduct a treatment group comparison (ONBOARD vs. CGM-only) of the change in A1c, the primary outcome, from baseline to 3, 6, and 12 months. Specifically, we will use linear mixed models to model changes in A1c as a function of time, intervention assignment, and group-by-time interaction. These models will include a subject-specific random effect to account for the correlation of

outcomes over time within a subject. We will examine change from baseline for each outcome as the dependent variable. We will begin by fitting models with minimum covariates prior to considering additional covariates. Similar models will be used to examine secondary outcomes of time in range, days of CGM wear (Hypothesis 1), diabetes distress, and perceived CGM benefit (Hypothesis 2). We will reference information criteria (e.g., Akaike's) to inform model selection decisions. Beyond testing the groups-by-time interaction term, custom contrasts will assess group differences at each time point. Exploratory analyses will examine differences between subgroups over time after primary, intent-to-treat analyses are completed. Additional exploratory analyses will examine patient-level predictors of CGM wear (e.g. age, gender, diabetes duration). For the CGM-continuer subgroup, we will conduct exploratory longitudinal analyses using CGM data to look at changes in time in range. We will adjust for multiple comparisons by using the Benjamini-Hochberg procedure and a false discovery rate of 0.05 (78). Analyses will initially be conducted without imputation for missing values, using the missing-at-random approach (79) and then multiple imputation will be used to supply values for missing data. We will conduct sensitivity analysis by multiple imputation to compare the effects.

Enrolling and randomizing a sample of 178 adults with T1D (1:1 randomization; 89 per arm) will be sufficient to investigate the hypotheses in this study. Based on our previous related work, we estimate 15% attrition, yielding a final sample size of 76 participants per arm (152 total). This target sample size is based on the following pieces of data. First, effect sizes comparing CGM to non-use in adults with T1D are in the moderate ($d=.40\text{--}.50$) range (8, 75, 76), showing improvements in A1c and time in range during CGM use. Further, standardized effects of diabetes behavioral interventions for adults are in the small to moderate range with .35 to .40 SD unit differences (43, 77). In the proposed study, we hypothesize group differences in A1c of a similar or greater magnitude will be driven by a combination of greater sustained use of CGM over the 12-month follow-up period in the ONBOARD program and added utility and benefits from use resulting from the ONBOARD program. Sample size estimates for comparison of ONBOARD and CGM-only are based on intent-to-treat analyses, $\alpha=.05$, 80% power, autocorrelation of .50 (7), a repeated measures ANOVA on change between the 2 groups from baseline to 3, 6 and 12 months. A sample of 89 participants assigned to ONBOARD and 89 to CGM-only will provide power to exceed 0.80 for the primary outcome of A1c for moderate effects of $d=.35$ or greater. The sample size allows detectable mean differences in the magnitude of $A1c \geq 0.5\%$ (conservatively assuming 1.2 SD; recent registry data suggests our SD will be closer to 1.0). A 0.5% A1c is the minimum clinically significant difference regarded by physicians and stakeholders. Treatment guidelines and algorithms from ADA/EASD and UK National Institute for Clinical Excellence have recommended evaluating new treatment regimens by whether A1c is lowered by 0.5% or more. Between clinic and wider T1D community, we will have ample ability to reach our recruitment goal.

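### The single subject random effect in section 2.7 gives all three A1c visits one pooled variance, so the visit-specific group contrasts have wrong standard errors if the variance of change differs by visit

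*Combined protocol and SAP*

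**What the plan says.** Section 2.7 specifies linear mixed models for A1c with time, group and their interaction. The dependent variable is stated: "We will examine change from baseline for each outcome as the dependent variable". The only term for within-person correlation is introduced by "These models will include a subject-specific random effect to account for the correlation of" outcomes in the same person. The section gives no residual covariance structure, no visit-specific variance, no robust standard error and no degrees-of-freedom method.

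Beyond the interaction test, "custom contrasts will assess group differences at each time point". On model choice the section adds "We will reference information criteria (e.g., Akaike's) to inform model selection decisions", without saying whether this extends to the covariance structure.

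The sample-size paragraph of 2.7 uses one SD (1.2, perhaps nearer 1.0) and an "autocorrelation of .50 (7), a repeated measures ANOVA on change between the 2 groups from baseline to 3, 6 and 12 months". Section 2.3 requires CGM use in both arms for 12 weeks and then says: "After that time period, they can continue or discontinue use of CGM".

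**The concern.** A lone subject random effect, read in the usual way as an intercept with independent residuals of equal variance, implies compound symmetry for the three changes. Every visit contrast is then judged against the same standard error, built from the average variance over visits. If the true variance of change at a visit is below that average, the test there is conservative and loses power. If it is above, the test rejects too often and the interval is too short.

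Equal variance cannot be taken for granted here. Everyone must wear CGM up to about the first follow-up visit and may stop afterwards, so a wider spread of A1c change at 6 and 12 months is plausible. An autocorrelation that decays with time since baseline would have the same effect. The 3-month comparison is the initial one described in section 2.1, and 12 months is the last follow-up, so the two visits most exposed are also of most interest. The resulting p-values would also feed the planned Benjamini-Hochberg procedure.

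**Working it through.** **Inputs.** From 2.7: 89 randomised and 76 completers per arm, d = .35, alpha .05 (two-sided assumed; the plan does not say), correlation .50, follow-up at 3, 6 and 12 months. Assumed, because the documents do not give them: how the variance of change behaves over the visits. Complete data are assumed throughout.

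**The plan's own figure.** Take a between-group test on the average of three equally correlated visits. The SD factor is √[(1 + 2 × .50)/3] = .816, and the SE is .816 × √(2/89) = .1224 SD units. Then .35/.1224 = 2.86, and power = Φ(2.86 − 1.96) = .816. The claim of power above .80 with 89 per arm reproduces, under constant correlation.

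**Effect of the pooled variance.** With complete data the random-intercept model estimates the variance at every visit as the mean of the visit variances. So

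- SE ratio (model to true) at visit t = √(mean variance / variance at t)
- actual type I error = 2 × [1 − Φ(1.96 × ratio)]

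Only the equal-variance restriction enters these formulas. The equal-correlation restriction matters for the interaction test, for between-visit contrasts and, with about 15% attrition, for the missing-at-random analysis.

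**Illustration: raw A1c, equal SDs, correlation .50 per visit step.** Correlations with baseline are .50, .25 and .125. Variance of change is 2 × (1 − correlation), in units of SD squared: 1.00, 1.50, 1.75, with mean 4.25/3 = 1.417.

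| Visit | SE ratio | Type I error | Simulated |
|---|---|---|---|
| 3 months | √(1.417/1.00) = 1.19 | .020 | .021 |
| 6 months | √(1.417/1.50) = 0.97 | .057 | .055 |
| 12 months | √(1.417/1.75) = 0.90 | .078 | .078 |

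The simulation used 20,000 trials of 76 per arm. Visit-specific variances gave .047 to .050 at the three visits in the same simulation.

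Power at 3 months for d = .35: true SE = √(2/76) = .162, and .35/.162 = 2.16. With the correct SE, Φ(2.16 − 1.96) = .58 (.57 by simulation). With the pooled SE, Φ(2.16 − 1.96 × 1.19) = Φ(−.17) = .43.

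**Other patterns**

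| Assumed pattern | SE ratio 3 / 6 / 12 months | Type I error 3 / 6 / 12 months |
|---|---|---|
| Equal variances of change | 1.00 / 1.00 / 1.00 | .05 / .05 / .05 |
| Correlation with baseline decaying to .50 at 12 months | 1.41 / 1.04 / 0.80 | .006 / .041 / .118 |
| SDs of change falling, 1.2 : 1.0 : 0.8 | 0.84 / 1.01 / 1.27 | .098 / .047 / .013 |

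Decay is not needed for an error to appear. With constant correlation .50 and raw SDs of 1.0, 1.0, 1.15 and 1.3 from baseline to 12 months, the variances of change are 1.00, 1.1725 and 1.39 (for example 1 + 1.69 − 1.30 = 1.39), with mean 1.1875. The ratios are 1.09 at 3 months and 0.92 at 12 months. Simulated type I error is 3.2% and 7.0%, and 3-month power is .51 instead of .57.

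**The case against.** The strongest reply is that nothing in the documents shows the variance of change growing. There is one SD and one correlation. The .50 is given alongside an ANOVA on change and may describe correlation among the changes themselves. Even if that correlation decays, equal SDs of change leave all three SE ratios at 1.00. The plan's power figure also reproduces under constant correlation. Optional CGM after 12 weeks is a reason to expect wider spread, not a measurement of it. All of this stands. A reader might infer that the 3-month test is conservative and the 12-month test anti-conservative; the documents do not support that as a fact about this trial.

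A second reply is that the information-criteria sentence may let the analysts leave compound symmetry, so the model is not strictly forced. In a simulation of 3,000 trials per scenario, AIC chose the unstructured form over compound symmetry more than 99% of the time under decaying correlation, and type I error returned to .046–.059. With the milder unequal SDs it did so 59% of the time, leaving the 12-month error near .06. So the larger errors arise only if that step excludes covariance structure. But the sentence does not say that it includes it, and choosing the primary covariance from the trial data is weaker than fixing it beforehand.

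Third, the power loss concerns a single visit contrast, whereas the plan's power statement is for a repeated-measures analysis over all visits, with visit contrasts in addition to the interaction test. That is right, and the .43 should not be set against the plan's .80.

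**Conclusion.** The point holds in conditional form. On its ordinary reading the stated model gives the three visit contrasts one shared standard error, which is correct only if the variance of change is the same at each visit. If the .50 applies to raw A1c and decays by visit step, the error is material at both ends of follow-up: 19% too wide at 3 months and 10% too narrow at 12. If the variances are equal there is no error, and if they fall the direction reverses. These figures assume complete data, 76 per arm and two-sided testing. The variance patterns are illustrations, not estimates from this trial. The change is worth making because one specification covers all the patterns and costs almost nothing when it proves unnecessary.

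**What to change.** In section 2.7, replace the single subject-specific random effect in the primary model with a repeated-measures specification:

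- visit as a categorical factor, with group and group-by-visit;
- an unstructured covariance over the 3-, 6- and 12-month changes;
- Kenward-Roger or Satterthwaite degrees of freedom;
- heterogeneous compound symmetry as the named fallback if the model does not converge, since it still allows a separate variance at each visit;
- a statement that information criteria will not be used to choose the primary covariance structure.

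The cost is a few lines of wording and six covariance parameters instead of two, for about 152 to 178 participants, with a negligible loss of degrees of freedom. If compound symmetry is true, simulated 3-month power for d = .35 is .57 under either model.

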2.1. Synopsis of study protocol

The primary objective of this randomized controlled trial is to examine the impact of a behavioral support intervention for adults with type 1 diabetes (T1D) who are starting on continuous glucose monitoring (CGM). This trial compares adults with T1D who are starting on CGM with behavioral supports (the intervention group) versus those who are starting on CGM without behavioral supports (the control group). We will examine group differences over a 3-month period on two sets of outcomes. The first set of outcomes includes glycemic variables (e.g. hemoglobin A1c, time in range). In this set of outcomes, A1c is the identified primary endpoint. The second set of outcomes includes psychosocial variables (e.g. diabetes distress, worry about hypoglycemia, technology attitudes), with diabetes distress as the primary endpoint. After the initial comparison of intervention to control across the first 3 months after starting CGM, we will conduct a longitudinal follow-up of glycemic and psychosocial outcomes at 6 and 12 months.

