2.2. Study procedures

Participants will be recruited at Stanford University through a combination of in-clinic, in community locations and online through type 1 diabetes online communities. Eligible participants will be adults (ages 18-50) who have not been using CGM consistently (>5 days/week) for at least the past 6 months. Once identified in clinic or once someone has expressed interest in the study, study staff will approach potential participants to explain the study, determine eligibility, and obtain informed consent. All participants will complete their baseline visit remotely. This baseline visit will include 1) completing a hemoglobin A1c test kit that is mailed to them in advance; 2) completing a baseline assessment survey online via a secure site (REDCap) to obtain demographic and psychosocial data and 3) initiate use of CGM supplies. Participants will be given the choice of using Dexcom G6 or Libre 2 CGM. Participants will be mailed 12 weeks of CGM supplies of their choice and will receive initial standard CGM introduction and education from the study staff and will be provided with standard resources from the device manufacturer at this baseline visit. At baseline, participants will then be randomized. We will randomize at a 1:1 ratio, intervention to control. Those randomized to the intervention (ONBOARD) condition will schedule 4 60-minute sessions with study interventionist (every 2 weeks), with the first session scheduled for 2 weeks after CGM initiation. Sessions will be conducted via a secure, HIPAA-compliant, videoconferencing software (Zoom) and may be recorded to ensure consistency and quality of the intervention across participants and interventionists. Each participant will receive one unique Zoom link that they will use for all 4 of their study sessions. At the 3-, 6-, and 12-month time points, participants will be mailed A1c test kits for follow-up A1cs, and will complete a follow-up REDCap survey at these time points as well. The follow-up survey will assess psychosocial variables, technology satisfaction, and changes to demographic/medical information. Each follow-up survey is expected to take 30 minutes to complete. Of note, all study participants will

receive instruction on how to work with their insurance to obtain coverage for continuing to use CGM after the first 12 weeks of the study. At the 3-, 6-, and 12-month timepoints, CGM data downloads will be obtained.

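### The A1c model analyses change from baseline without naming baseline A1c as a covariate; this is valid, but it gives up precision that adjustment would recover (25% of the 3-month variance if the plan's .50 is the baseline to follow-up correlation).

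*Combined protocol and SAP*

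**What the plan says.** Section 2.7 describes the A1c analysis in these words: "we will use linear mixed models to model changes in A1c as a function of time, intervention assignment, and group-by-time interaction". A subject-specific random effect is included, and contrasts are taken between arms at each time point. The dependent variable is fixed for every outcome: "We will examine change from baseline for each outcome as the dependent variable".

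On covariates the section says only this: "We will begin by fitting models with minimum covariates prior to considering additional covariates". It does not say what the minimum is, which others may follow, or on what criterion. Information criteria are to guide model selection, with no limit on which decisions they govern.

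The sample-size paragraph of 2.7 rests on "autocorrelation of .50 (7), a repeated measures ANOVA on change between the 2 groups from baseline to 3, 6 and 12 months", with 89 per arm randomized, 76 per arm after 15% attrition, and d = .35. It does not say which pair of measurements the .50 correlates.

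The synopsis (2.1) puts the initial comparison at three months: "We will examine group differences over a 3-month period on two sets of outcomes". Section 2.2 has each participant "completing a hemoglobin A1c test kit that is mailed to them in advance", with randomization following, so a pre-randomization A1c is already part of the design.

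**The concern.** Subtracting the baseline value is a fixed adjustment with a slope of 1. Regression on baseline estimates the slope, which is about ρ when SDs are equal. For any ρ below 1 the fixed slope is too steep, and the change score carries baseline noise into the treatment contrast. At ρ = .50 the change score is no more precise than the follow-up A1c alone, so nothing is gained from having measured baseline.

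This matters most at 3 months. A single-visit contrast does not benefit from averaging over three visits, and that averaging is what carries the plan's sample-size calculation above 0.80.

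There is also a pre-specification side. Baseline A1c might enter as part of the minimum, might enter later, or might never enter. Each choice gives a different primary estimate, and all are compatible with 2.7 as written.

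**Working it through.** **Inputs from 2.7.** Randomized 89 per arm; 76 per arm after attrition; α = .05 (two-sided assumed); d = .35; a 0.5% difference with SD 1.2 (conservative) or about 1.0; correlation .50. Assumptions added here: equal A1c SD at all visits, equal correlation ρ between visits, complete data, d in A1c SD units. Power uses the noncentral t distribution with SE = SD × √(2v/n), where v is the per-person variance in units of SD².

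**The plan's own figure.** For the mean of three change scores, v = (1 + 2ρ)/3 + 1 − 2ρ. At ρ = .50 this is .667. With n = 89, SE = √(2 × .667/89) = .122, and .35/.122 = 2.86. Power is 0.81, so the stated figure above 0.80 reproduces. At 76 per arm it is 0.75.

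**One visit.**
- Change score: v = 1 + 1 − 2ρ = 2(1 − ρ).
- Adjusted for baseline: v = 1 − ρ².
- Ratio: (1 − ρ)(1 + ρ) / [2(1 − ρ)] = (1 + ρ)/2.

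Results at 3 months, d = .35, 76 per arm:

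| ρ | v, change | v, adjusted | Variance saved | Power, change | Power, adjusted |
|---|---|---|---|---|---|
| .3 | 1.40 | .91 | 35% | .44 | .61 |
| .5 | 1.00 | .75 | 25% | .57 | .70 |
| .7 | .60 | .51 | 15% | .79 | .85 |
| .8 | .40 | .36 | 10% | .92 | .95 |

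At 89 per arm and ρ = .5, power goes from .64 to .76. To match the adjusted precision of 76 per arm, change scores would need 76/.75, about 101 per arm.

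**On the A1c scale, 3 months, ρ = .5, difference 0.5%.**
- SD 1.2, 76 per arm: SE 1.2 × √(2/76) = 0.195 falls to 1.2 × √(1.5/76) = 0.169. Power goes from .72 to .84, and the 95% half-width from 0.38% to 0.33%.
- SD 1.2, 89 per arm: power .79 to .89.
- SD 1.0, 76 per arm: power .865 to .94.

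**Average of three visits, ρ = .5.** Adjusted v = (1 + 2ρ)/3 − ρ² = .667 − .25 = .417, a ratio of .417/.667 = .625. Power at d = .35 goes from .75 to .91 (76 per arm) and from .81 to .95 (89 per arm).

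**Simulation.** With 3000 runs, d = .35, ρ = .5 and 76 per arm, 3-month power was .579 for change and .707 adjusted. Mean estimates under both methods were within .003 of the true .35, so neither is biased. In a fit of the full three-visit model (4000 runs, 89 per arm), the 3-month variance ratio was .75 when visits were equally correlated. With correlation decaying over visits (AR(1) at .50) it was .751 with a separate baseline slope per visit and .774 with one common slope. This is the reason for a baseline-by-visit term.

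**Sensitivity to equal SDs.** Let k be follow-up SD divided by baseline SD. The change variance is 1 + k² − 2ρk and the adjusted variance k²(1 − ρ²). At ρ = .5, k = 1.25 gives 1.3125 against 1.172 (11% saved) and k = 0.8 gives .84 against .48 (43% saved). At ρ = .8 and k = 1.25 both are .5625 and nothing is saved.

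**The case against.** The strongest reply is that the plan contains no error. The change-score contrast is unbiased, the power claim reproduces, and nothing in 2.7 forbids adding baseline A1c later. All of that stands, and for that reason this is a recommendation about efficiency and pre-specification.

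The second reply is that the 25% is fragile.
- If all visits are equally correlated, change scores that share a baseline correlate .50 whatever ρ is. The plan's .50 may describe those change scores and so leave ρ unknown. At ρ = .8 the saving is only 10%.
- The size also depends on equal SDs, as shown above, and the documents give no SD by visit.
- If d = .35 is in SDs of change, unadjusted power at 76 per arm is .57 at every ρ, and adjustment gives .76, .70, .64 and .62 at ρ = .3, .5, .7 and .8.

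These points make the size uncertain. They do not reverse the direction: apart from the few degrees of freedom spent, adjustment does not lose precision in any of these cases.

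Third, 2.7 does not say when the 15% attrition accrues, so the number available at 3 months may lie between 76 and 89 per arm. At 89 per arm with SD 1.2, unadjusted power for 0.5% is already .79; at SD 1.0 it is .91. The need is then less pressing, although the gain remains.

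Finally, naming a baseline covariate does not settle which time point is primary, or how CGM-derived outcomes should be modelled. Those are separate questions.

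**Conclusion.** The point holds. The planned analysis is valid and its stated power is correct, but the primary A1c contrast is less precise than the same data allow, and the covariates for the primary estimate are not fixed in advance. With equal SDs and ρ = .50, adjustment removes 25% of the variance at 3 months, which shortens the standard error by 13% (√.75 = .866). The saving is 35% to 10% for ρ from .3 to .8. In the plan's conservative setting (0.5%, SD 1.2, 76 per arm, ρ = .50), it moves 3-month power from below 80% to above it. The amount depends on ρ, on the SDs by visit and on the number retained. The case for naming the covariates does not depend on any of these. The change should be made, but the trial is not unsound without it.

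**What to change.** In 2.7, define the primary model as A1c at 3, 6 and 12 months with fixed effects for baseline A1c, baseline-by-visit, arm, visit and arm-by-visit, and report the adjusted arm difference at each visit. Change may stay as the dependent variable if preferred: once baseline and baseline-by-visit are in the model, the arm differences are identical, because subtracting baseline only lowers each baseline slope by 1. State how within-subject correlation is modelled.

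Use the same form, with the baseline score, for diabetes distress and other scales that have a true pre-treatment value. Do not carry it over automatically to time in range or CGM wear. Section 2.5 says "Baseline is the date they complete their first assessment and begin using their CGM", so a pre-CGM value of those measures may not exist, and they need their own definition.

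List every covariate before any outcome data are examined, and limit information criteria to the choice of covariance structure. In the sample-size paragraph, say which measurements the .50 links.

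The cost is a short rewrite of one paragraph and a few degrees of freedom. No visit or measurement is added, and no participant is lost, because a change score already requires the baseline value.
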